6.1.3 Other Methods

No other methods are used.

6.2 Procedure for unblinding (code break)

There is no provision for the statistician to be blinded.

6.3 Procedure for unblinding (code break)

Blinding (coding) of study participants is only permitted if an unforeseen incident or medical problems occur during or after the completion of study participation in a subject, which may be attributable to participation in the study.

For incidents (AE) that occur during or shortly after the simulated altitude (within the first 24 hours) and can potentially be attributed to the intervention, the principal investigator may, at his or her discretion, immediately waive the blinding of the study participant and the investigators present to ensure adequate treatment of the study participant.

In the case of incidents (AE) that occur longer than 24 hours after the simulated altitude, clarification with a doctor is mandatory and a doctor's certificate is required for the lifting of blindness. Data may then also be passed on to the attending physician with the consent of the study participant concerned. This approach is justified because no life-threatening incidents are to be expected due to the intervention used here.

SUPSI

SUPSI

7 STUDENT POPULATION

7.1 Inclusion Criteria

Inclusion Criteria

- Healthy, adult aged 18 to 50 years
- No cardiovascular diseases and/or interventions
- no surgical interventions on the cardiovascular system.
- No current injuries and/or pain conditions
- Regular and sufficient sleep
- No terrestrial altitude of 1000 m exceeded in the last month (including flights)
- Not exposed to any form of hypoxia in the last month
- Signed consent form

Exclusion criteria

- Age over 50 years
- Current injuries of any kind and/or pain conditions
- Acute and/or chronic pain conditions
- Known general diseases (e.g. diabetes mellitus)
- Fear of hypoxia
- Fear of heights or sensitivity to terrestrial altitude
- Regular intake of medication (including self-purchased medication), with the exception of contraception drugs
- Cardiovascular disease or abnormalities
- Abnormalities of blood analysis or ECG
- Mental illnesses
- Pregnancy / breastfeeding
- Cognitive / linguistic inability to understand the study information or the study action.

7.2 Recruitment and Screening

Recruitment

It is advertised on the websites (homepage & Facebook) of "Thim van der Laan" and "SUPSI". In addition, information posters will be hung up in the school building. The exact texts have been prepared according to the checklist of the Cantonal Ethics Commission Zurich.

As advertisements (text visible):

- Homepage of the Physioschule Thim van der Laan: www.physioschule.ch and SUPSI: www.supsi.ch
- Facebook page of the Thim van der Laan Physiotherapy School: <https://www.facebook.com/physioschule> and SUPSI: <https://www.facebook.com/supsi.physiotherapie/>

Screening

During the first contact, the potential participants are informed about the course and risks of the study, as well as the conditions for and the amount of compensation explained. A checklist for contacting them

SUPSI

by telephone serves as a basis.

During the first telephone contact, a questionnaire is filled out by the study management to determine the suitability as a study participant.

The checklist for the initial determination of suitability during the initial telephone contact can be found in the attachments. The advertisements and health questionnaires are also in the inserts.

7.3 Allocation of situations

The situation assignment (normobar & normoxic vs. normobar & hypoxic) is done concealed by means of a lot in a sealed envelope, which is drawn under the supervision of the study leader. This lot shows whether the subject first goes through the normobaric & normoxic situation or the normobar & hypoxic situation.

7.4 Discontinuation of study participation

If a participant withdraws from the study, the lot of the allocation is returned to the pot in a new envelope and a new participant is sought.

All data collected to date will be evaluated as far as possible and included in the data analysis (in accordance with Art. 9 ClinO). After evaluation, the data is irreversibly anonymized.

The conditions for the termination of the experiment were described in chap. 5.4.

There is no disadvantage for the participants if they discontinue their participation in the study.

SUPSI

8 STUDY INTERVENTION

8.1 Medical Device ID

8.1.1 Intervention product

The intervention product is a certified product. With the Cloud 9, a simulated altitude of 2700 m and 3530 m above sea level can be achieved. This corresponds to an oxygen partial pressure of 15.0% and 13.5%, respectively. The Cloud 9 altitude training device is intended for everyone (even amateurs) who wants to increase their performance. The Cloud 9 is a solid, certified product that complies with the European Directives on Electromagnetic Compatibility, Machinery Directive, Air Pressure Equipment and Low Voltage Equipment (89/336/EEC, 91/368/CEE, 93/68/CEE, 97/23/EC, EN61010-1).

Securing the test subjects

Only subjects who have completed the health questionnaire without risk factors will be admitted to the study. In this way, risk factors are detected at an early stage and the subjects for the study are not recruited. In addition, a doctor is present during the measurements to ensure the safety of the test subjects.

8.1.2 Control intervention

The control group will be observed under normobaric and normoxic conditions.

8.1.3 Packaging, labeling and use

The Cloud 9 is a solid, certified product that complies with the European Directives on Electromagnetic Compatibility, Machinery Directive, Air Pressure Equipment and Low Voltage Equipment (89/336/EEC, 91/368/CEE, 93/68/CEE, 97/23/EC, EN61010-1).

8.1.4 Storage

The Cloud 9 can be stored both outside in the dry and inside a room. The equipment is located inside our laboratory for the duration of the measurements and is only accessible to laboratory staff. The room in which Cloud 9 is located is fully ventilated and has the following dimensions: 7m x 14m x 2.5m.

8.2 Administration of the experiment

Since no prescription drugs or invasive methods are used, the experiment is not discussed further in chapters 8.2-8.4 and only chapter 9 is referred to.

8.2.1 Experimental intervention

Simulated height: The test subjects are in the laboratory of our institution and are connected to Cloud 9 by means of a mask. The subjects are exposed to a simulated altitude of 3530 m above sea level under normobaric conditions. This intervention is used to determine the psychophysiological effect under normobaric and hypoxic conditions.

Terrestrial altitude: The subjects are at an SAC hut (Bergrestaurant Hohsaas: <https://www.hohsaas-bergrestaurant.ch>) in the canton of Valais at an altitude of 3200 m above sea level. By means of this

SUPSI

exposure, the psychophysiological effect under hypobaric and hypoxic conditions is determined. The test subjects spend a single night in this SAC hut and the measurements are repeated the next day.

8.2.2 Control intervention

Control: The test subjects are in our laboratory under normobar and normoxic conditions. This situation serves as a control intervention, which is contrasted with the simulated and terrestrial situation.

8.3 Dosage, application modification

In the simulated altitude situation, the recommendations in the Cloud 9 operating manual are followed.

8.4 Adherence to the study intervention

The test subjects are neither motivated nor unnecessarily distracted by the examiners or the study director with conversations. Communication is kept to a minimum, only study-related discussions are conducted in order not to influence the psychophysiological effects and to ensure homogeneity.

8.5 Follow-up treatment of eliminated participants

Data already collected from eliminated participants is stored anonymously in the filing cabinet provided for this purpose. As far as possible, the data will be included in the data analysis of the study.

There is no disadvantage for the participants if they discontinue their participation in the study and no further interventions are necessary for follow-up treatment.

If study participation was discontinued due to a reaction occurring during study participation, this will be logged and reported to the sponsor investigator (head of the research laboratory), study leader and supervisor of the study. If medical care is necessary, the report is forwarded to the business liability insurance of Thim van der Laan AG (Basler Versicherung) in order to ensure the appropriate follow-up treatment.

8.6 Preventive measurements

Through the telephone assessment and the health questionnaire, the intake of medication, injuries and operations, as well as known relevant diseases and allergies are asked. In addition, only young and healthy subjects who have already been at this altitude and had no signs of altitude sickness are examined. Pregnant women or nursing mothers are not allowed to participate in the study. Subjects who assure the study leader that they are not pregnant are allowed to participate in the study. In case of uncertainty, the potential test subjects are provided with a pregnancy test free of charge. The test subjects must then present a negative pregnancy test (given away free of charge by us). The test result is noted on the health questionnaire.

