
Preparation
	
Subject recruitment
 
The subject information and declaration of consent are submitted. Questions may be asked. If the subject agrees with the information, he or she will be summoned to the first day of contact.
 
This includes the explanations on site, the signature of the declaration of consent and the completion of the health questionnaire. The pregnancy test must be negative (women only). If all tests are passed, an appointment is made for the intervention.
 
Test Subject Preparation Measurement Day
 
The test subject lies down on a couch in his underwear. This is followed by the 20-minute room acclimatization phase in the same storage. The room temperature is kept as constant and neutral as possible (deviation of $\pm 2^{\circ}\text{C}$).

SUPSI

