9.2.2 Multiple visits

After contact has been made by telephone and suitability has been determined by telephone, the subject information and the declaration of consent are submitted for inspection and reading. If the subject agrees with the study conditions and criteria, he or she registers to make an appointment for the 1st contact day.

The 1st contact day includes, in the order described, the; On-site explanations, signing the consent form, completing the health questionnaire and taking the pregnancy test for female subjects. If these points are passed positively, an appointment is made for the actual measurement day (2nd-5th contact day).

1. On-site explanation and completion of the health questionnaire, 1st contact day

The subjects will be comprehensively informed about the process and possible risks before they are confirmed to participate in the study. The declaration of consent explains to them what their rights and obligations are when participating and that they may withdraw from participation at any time without giving reasons, without incurring any disadvantages as a result. More detailed information can be found in chapter 2.7. In addition, a health questionnaire is filled out to identify any risks. An initial selection

SUPSI

process of suitable test persons takes place. If the health form has been completed and no risks have been identified, the test subjects are summoned to the 2nd day of contact.

2. Measurement, 2nd-5th day of contact

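### Section 8.6 admits women on a verbal assurance that they are not pregnant, while the synopsis and section 9.2.2 require every woman to pass a pregnancy test first

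*Combined protocol and SAP*

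**What the plan says.** The synopsis (exclusion criteria), the exclusion list in section 7.1 and section 8.6 all bar pregnant women. The sections differ on how pregnancy is to be ruled out.

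- **Section 8.6** accepts a statement from the subject: "Subjects who assure the study leader that they are not pregnant are allowed to participate in the study". It then adds "In case of uncertainty, the potential test subjects are provided with a pregnancy test free of charge", followed by "The test subjects must then present a negative pregnancy test (given away free of charge by us"). Finally, "The test result is noted on the health questionnaire".
- **The synopsis (Preparation)** sets a test requirement without any condition: "The pregnancy test must be negative (women only"). It continues: "If all tests are passed, an appointment is made for the intervention".
- **Section 9.2.2** lists the steps of the first contact day, among them "completing the health questionnaire and taking the pregnancy test for female subjects". The next sentence makes further participation depend on them: "If these points are passed positively, an appointment is made for the actual measurement day (2nd-5th contact day").

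Section 9.1.5 also mentions, in a parenthesis, a pregnancy test for female subjects as part of the health questionnaire.

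**The concern.** Under 8.6 a verbal assurance is enough for entry. Under the synopsis and 9.2.2 it is not. An assurance cannot detect a pregnancy that the woman does not yet know about, whereas a test can. Section 8.6 is the section on preventive measures, so a screener could reasonably take its rule as the operative one.

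What is at stake is participant safety and uniform eligibility. An untested woman could be exposed to hypoxia in the laboratory and to a night at altitude in spite of the exclusion criterion. Two screeners could also apply different entry rules, each with support in the text, and a monitor could not say which of them had deviated.

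**Working it through.** No figure in the plan needs to be reproduced here. The check is a comparison of the text, plus a count of the sessions that the exclusion is meant to protect.

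**1. The rules side by side**

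| Place | Who is tested | What entry depends on |
|---|---|---|
| 8.6 | Those about whom there is uncertainty | Assurance to the study leader, or a negative test in case of doubt |
| Synopsis, Preparation | All women | All tests passed before the appointment |
| 9.2.2 | All female subjects, first contact day | All steps passed before the appointment |
| 9.1.5 | Female subjects (parenthesis only) | No entry rule stated |

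**2. A test case.** Take a woman who assures the study leader that she is not pregnant, raises no doubt and is not tested. Under 8.6 she may take part. Under the synopsis and 9.2.2 no appointment may be made for her. The rules give opposite answers for the same person, so the conflict is one of substance.

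**3. Can 8.6 be read as a test for everyone?** The demand for a negative result is introduced by the word *then* and comes directly after the sentence on uncertainty, so its natural scope is the doubtful cases. If it applied to every woman, the assurance sentence would have no effect.

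**4. Does another section settle it?**
- Section 8.2 refers the reader to chapter 9, but only for 8.2 to 8.4. Section 8.6 lies outside that range.
- Section 7.1 lists pregnancy as an exclusion but does not say how it is verified.
- Section 8.1.1 admits only subjects whose health questionnaire shows no risk factors. This is not an independent safeguard: under 8.6 a test result reaches the questionnaire only if a test was done, so a woman who gave an assurance could pass it untested.

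**5. Exposure per participant (9.1 and 8.2.1)**
- Sessions: 1 simulated + 2 terrestrial + 1 control = 4. This agrees with the second to fifth contact days in 9.2.2 and with the stated total time: 30 + 4 × 110 = 470 min.
- Sessions at altitude: 1 (3530 m, simulated) + 2 (3200 m, terrestrial) = 3 of 4, with one night at 3200 m between the two terrestrial sessions.

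**The case against.** The strongest reply is that the protocol already handles this. Section 9.2.2 is the step-by-step visit procedure, and both it and the synopsis make the appointment depend on the test. An untested woman enters only if staff skip a listed step and rely on a more general section. That stands, and it is why the practical risk is modest.

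A second reply is that 8.6 may describe a first filter at the telephone stage, with the test following on the first contact day. The section does open with the telephone assessment, and it repeats the remark that the test is free, as if stating a separate rule. But 8.6 says that assured subjects may take part in the study, not that they proceed to further screening. This reading does not hold.

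Three smaller points are fair:
- The parenthesis in 9.1.5 is weak support, since it describes the content of the questionnaire and sets no entry rule. The real conflict is two places (synopsis and 9.2.2) against one (8.6).
- This is an internal inconsistency; no deliberate design choice is in dispute.
- A single test on the first contact day does not establish that a woman is not pregnant at a later altitude session, and the protocol sets no maximum interval between the two. Aligning the text leaves that gap open.

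**Conclusion.** The inconsistency is real and should be corrected. Section 8.6 sets a weaker entry rule than the synopsis and 9.2.2, and nothing in the protocol says which prevails. Anyone following 8.6 as written could send an untested woman to three altitude sessions and a night at 3200 m, although all sections agree that pregnant women must not take part.

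The matter is one of participant safety and eligibility. It has no bearing on sample size, power, type I error or the treatment comparisons. No size of clinical risk is claimed, because the documents give no basis for one.

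The conclusion rests on the protocol text alone. The health questionnaire and the telephone checklist are attachments that were not available, so actual screening practice cannot be judged.

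**What to change.** In 8.6, keep the sentence that bars pregnant women and nursing mothers. Replace the four sentences after it with one:

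> Every female subject must have a negative pregnancy test on the first contact day, before a measurement appointment is made; the test is supplied at no cost and the result is recorded on the health questionnaire.

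This adopts the stricter rule already in the synopsis and 9.2.2. Stating the conditional rule everywhere would also remove the conflict, but with less protection.

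**Cost.** One inexpensive test per woman attending the first contact day. That is no more than the synopsis and 9.2.2 already plan; tests are added only where staff would otherwise have followed 8.6. The documents do not give the number of women screened, so no total is stated.

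**Approval.** Section 2.3 does not permit protocol changes without prior consent of the ethics committee, apart from removing immediate hazards, and section 2.10 requires review of significant changes. Because the amendment alters an entry check, it is safer to submit it for consent before use than merely to notify it.

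When making the change, the sponsor could also consider a maximum interval between the test and the altitude sessions, or a repeat test. That would be an addition to the present plan and is not needed to resolve the inconsistency.

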8.7 Accompaniments

No further side effects are expected from study participation. However, a doctor is present to detect unexpected side effects and react accordingly.

SUPSI

8.8 Liability

The experiments are taking place in the research laboratory of the "Physiotherapie Graubünden" in Landquart and in the Hohsaas mountain restaurant (canton of Valais). The liability for the transport is assumed by the business liability insurance of Thim van der Laan AG (Basler Versicherung).

8.9 Return of the medical device

Cloud 9 was purchased by the research department of the "University of Applied Sciences and Arts Southern Switzerland" and will remain in the research laboratory after the measurements have been completed.

SUPSI

9 STUDY STRUCTURE & EVALUATION

9.1 Schedule Study Protocol

1. Subject Information & Informed Consent

30 min

2. Preparation of the subject

20 min

3. Running the Test Log (Sublogs)

Test protocol: Time required – maximum 90 min		
Normobar hypoxic vs. hypobar hypoxic vs. normobar normoxic		
Simulated Height (Cloud 9)	Terrestrial Altitude	Control intervention
1.) Baseline measurements Perfusion Microcirculation Oxygen Saturation Muscle & Brain Oxygen saturation of blood Blood Pressure & Heart Rate Skin temperature Lactate & Creatine Kinase Balance measurement Pain sensation Psychological measurements Thermal comfort & temperature perception 20 min	1.) Baseline measurements Perfusion Microcirculation Oxygen Saturation Muscle & Brain Oxygen saturation of blood Blood Pressure & Heart Rate Skin temperature Lactate & Creatine Kinase Balance measurement Pain sensation Psychological measurements Thermal comfort & temperature perception 20 min	1.) Baseline measurements Perfusion Microcirculation Oxygen Saturation Muscle & Brain Oxygen saturation of blood Blood Pressure & Heart Rate Skin temperature Lactate & Creatine Kinase Balance measurement Pain sensation Psychological measurements Thermal comfort & temperature perception 20 min
2.) Step-up task 5 min	2.) Step-up task 5 min	2.) Step-up task 5 min
3.) Follow-up Perfusion Microcirculation Oxygen Saturation Muscle & Brain Oxygen saturation of blood	3.) Follow-up Perfusion Microcirculation Oxygen Saturation Muscle & Brain Oxygen saturation of blood Blood Pressure & Heart Rate	3.) Follow-up Perfusion Microcirculation Oxygen Saturation Muscle & Brain Oxygen saturation of blood Blood Pressure & Heart Rate

SUPSI


Blood Pressure & Heart Rate Skin temperature Lactate & Creatine Kinase
 
10 min
 
3.) Cold water immersion of the hand
 
5 min
 
4.) Follow-up Perfusion Microcirculation Oxygen Saturation Muscle & Brain Oxygen saturation of blood Blood Pressure & Heart Rate Skin temperature Lactate & Creatine Kinase Balance measurement Pain sensation Psychological measurements Thermal comfort & temperature perception
 
40 min
	
Skin temperature Lactate & Creatine Kinase
 
10 min
 
3.) Cold water immersion of the hand
 
5 min
 
4.) Follow-up Perfusion Microcirculation Oxygen Saturation Muscle & Brain Oxygen saturation of blood Blood Pressure & Heart Rate Skin temperature Lactate & Creatine Kinase Balance measurement Pain sensation Psychological measurements Thermal comfort & temperature perception
 
40 min
	
Skin temperature Lactate & Creatine Kinase
 
10 min
 
3.) Cold water immersion of the hand
 
5 min
 
4.) Follow-up Perfusion Microcirculation Oxygen Saturation Muscle & Brain Oxygen saturation of blood Blood Pressure & Heart Rate Skin temperature Lactate & Creatine Kinase Balance measurement Pain sensation Psychological measurements Thermal comfort & temperature perception
 
40 min

---	---	---

Test log	Time exposure	Visits
Declaration of Consent	30 min	Unique
Simulated Height	20 + 90 min = 110 min	Unique
Terrestrial Altitude	20 + 90 min = 110 min	Twice (incl. 1x overnight stay)
Control intervention	20 + 90 min = 110 min	Unique
TOTAL TIME COMMITMENT	470 min + 1 night	

Each test subject can expect a total time expenditure of 470 minutes excluding the journey to and from Valais and the overnight stay at the SAC mountain hut.

9.1.1 Measurement of primary results

The primary measurements of perfusion of skin microcirculation, oxygen saturation of the muscles, brain, musculature as well as the measurement of blood pressure & heart rate, skin temperature, lactate, creatine kinase, pain sensation and balance can be measured within 10 min.

SUPSI

The psychological measurements, which are carried out on the basis of questionnaires, can be carried out within 10 minutes.

